8.6 Missing Data and Sensitivity Analyses (Primary Objective)

By design, the analysis of the primary objective (at both the interim and final time points) will predict 2-year outcomes for any subjects without measured 2-year outcomes, based on transitions from interim states and the experience of those who went on from those states to provide complete 2-year data. This is true whether the missing 2-year outcomes are due to being enrolled later in the trial (as happens for many subjects at the interim analysis) or some other cause, such as loss to follow-up (which will likely apply at both the interim and final analyses). Several additional analyses are planned which will explore the sensitivity of the main conclusions to this prediction for subjects whose missing 2-year outcomes cannot be explained by simply being enrolled late (i.e., subjects who are known to be lost to follow-up or whose 2-year visit window has closed without a measured outcome). In these analyses and for such subjects, 2-year outcomes will be imputed according to the model described below.

As with the primary analysis, any such subject will be viewed as belonging to one of several states. These are the same states used in the primary analysis:

- no interim data
- success at 6 months
- recoverable non-success at 6 months
- failure at 6 months
- success at 1 year
- recoverable non-success at 1 year
- failure at 1 year

Interim failures can be imputed to be failures at 2 years, with certainty. For each of the remaining states, the probability of becoming a responder at 2 years will be modeled via a logistic formulation. Based on the number S and F of subjects who went on from that state to become 2-year successes and failures, respectively, a logistic regression of the following form will be fit:

$$\text{logit}(p) = \beta_0$$

where the parameter β_0 will be assigned a vague $N(0, 10^2)$ distribution. The posterior distribution for β_0 will then be shifted by a biasing constant γ and will be back-transformed to the probability scale as:

$$p^* = \text{logit}^{-1}(\beta_0 + \gamma)$$

The 2-year outcome for any subject belonging to this state but lost thereafter will be imputed based on this distribution of p^* . The case $\gamma = 0$ contains no bias and corresponds essentially to the primary analysis.

By varying γ , we can examine the impact of a biasing influence on the study results. The values $\gamma = -\infty$ and $\gamma = +\infty$ correspond to setting all such observations to be failures or successes, respectively. The impact of various values of γ will be examined and presented in a sensitivity analysis, representing both positive and negative biases for the two groups.

[REDACTED]

[REDACTED]

[REDACTED]

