- Is of child-bearing potential, and is either pregnant or interested in becoming pregnant during the duration of the study;
- Medically significant obesity as defined by a Body Mass Index (BMI) of > 40 kg/m². BMI = (weight in pounds \times 703) \div (height in inches \times height in inches);
- Active malignancy: a history of any invasive malignancy (except non-melanoma skin cancer), unless the patient has been treated with curative intent and there have been no clinical signs or symptoms of the malignancy for at least 5 years;

- Known allergy to cobalt chromium or titanium;
- Used any investigational drug or device within the past 30 days;
- Pending litigation related to back pain or injury;
- Is a prisoner.

Primary Endpoint: The primary study endpoint for this study is individual patient success at 24 months. Individual patient success will be defined as follows:

- Improvement in the ZCQ by a minimum of 0.5 for both Symptom Severity (SS) and Physical Function (PF) scores at 24 months as compared to baseline.
- Maintenance or improvement in neurological outcome at 24 months.
- No subsequent surgical intervention at the level of treatment (including device failures requiring revision, removal, re-operation and supplemental fixation).
- No serious device-related adverse events.

Secondary Endpoints:

- Maintenance or improvement of the components of the primary ZCQ;
- Maintenance or improvement in patient function, as measured by the Oswestry Disability Index (ODI) questionnaire;
- Maintenance or improvement of the leg and back VAS pain scores;
- Maintenance or improvement in the components of the SF-36 Quality of Life Questionnaire;
- Changes in quantitative radiographic measures including disc height, vertebral range of motion and translation;
- Changes in qualitative radiographic measures including fusion; assessment, device migration and presence of radiolucencies;
- Radiographic Success
- Maintenance or improvement in neurological status;
- Incidence, severity and device or procedure relatedness of all adverse events over the 24-month study assessment period;
- Components of primary endpoint (surgical revisions, reoperations, removals, supplemental fixation);
- Return to normal activities of daily life;
- Change in work status and time to return to work;
- Narcotic medication usage;
- Length of hospital stay;
- Duration of surgical procedure and instrumentation time;
- Blood loss;
- Rehabilitation utilization.

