3.5 Study Endpoints

3.5.1 Primary Endpoint

The primary study endpoint for this study is individual patient success at 24 months. Individual patient success will be defined as follows and each component of the primary endpoint will be adjudicated by the Clinical Event Committee:

- Improvements in the ZCQ score by a minimum decrease of 0.5 versus baseline for both Symptom Severity (SS) and Physical Function (PF) scores.
- Maintenance or improvement in neurological outcome at 24 months.
- No subsequent surgical intervention at the level of treatment (including device failures requiring revision, removal, re-operation and supplemental fixation).
- No serious device-related adverse events (see paragraph below.)

[REDACTED]

[REDACTED]

[REDACTED]

[REDACTED]

[REDACTED]

[REDACTED]

[REDACTED]

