5.7 Patient Discontinuation

All patients enrolled into the current study and who have undergone one of the study treatments, will be followed for 24 months postoperative and until all FDA requirements are met, potentially up to 10 years postoperative. Acceptable reasons for not evaluating a patient through the follow-up period include:

- a) Patient Lost to Follow-Up: Unable to locate patient despite documented attempts to notify the patient via telephone and by certified mail. A patient will not be considered lost to follow-up until the last scheduled follow-up visit (24 month study time point).
- b) Patient Request to Terminate: The patient requests to terminate his/her involvement in the study, therefore withdrawing his/her consent to participate in the study (the investigator must thoroughly document the reasons for termination).
- c) Patient Death: If possible, an autopsy and/or death certificate should be obtained in order to document the cause of death.

If a patient discontinues from the study (regardless of the reason), the investigator will record the reason for withdrawal on the appropriate CRFs. Every effort shall be made to have discontinued patients (as appropriate) return for an “Early Termination Visit” to collect the required safety evaluations as detailed in the protocol.

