6.1.2 Relationship to Procedure

The relationship between an adverse event and the surgical procedure (investigational or control treatment) will be assessed on the basis of the following definitions:

- **Definitely Related:** Clear-cut temporal association and no other possible cause.
- **Probably Related:** Clear-cut temporal association and a potential alternative etiology that is not apparent.
- **Possibly Related:** Temporal association is less clear and other etiologies are also possible.
- **Probably Not Related:** Temporal association and the nature of the event is such that the surgical procedure is not likely to have had any association with the observed event (cause and effect relationship improbable but not impossible)
- **Definitely Not Related:** There is no temporal association and/or evidence exists that the event is definitely related to another etiology

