8.0 STATISTICAL ANALYSIS PLAN

8.1 Analysis Populations

Primary Analysis Population:

The principal analysis of the primary and secondary endpoints will utilize the intent-to-treat (ITT) patient population. The ITT population will include all randomized subjects for whom surgery is attempted. Subjects for whom surgery is attempted but not successfully completed will be considered treatment failures. Randomized subjects in whom surgery is not attempted will be described in detail in a separate section of the study report.

Secondary Analysis Populations:

The primary and secondary objectives will be further analyzed using an as-treated (AT) analysis performed on all randomized subjects according to the treatment actually received.

The primary and secondary objectives will be further analyzed using a per protocol (PP) analysis performed on an evaluable patient population. The evaluable population will consist of all ITT subjects that: [1] meet critical study eligibility criteria and have no significant protocol deviations based on Clinical Events Committee assessment; [2] have the assigned procedure completed; and [3] completed the 24-month follow-up assessment.

Training Population:

This patient population will include all non-randomized AFRS treated patients enrolled during the pivotal phase of the trial as training cases at the site. A maximum of two patients per site for a total of 60 patients will be included in this cohort. Training cases will be described separately from randomized patients in the final study report and will be presented primarily using descriptive statistics. This patient population will be used to understand the learning curve in the use of the device by assessing the results of the Training cases relative to those obtained in the Treatment group arm of the randomized study.

An additional presentation of the safety data in which all of the patients treated with the AFRS device (non-randomized and randomized) are combined as one cohort and compared to the control group will be included.

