Narcotic Medication Usage

The proportions of subjects in each treatment group who are not on narcotic pain relieving medications and in whom an epidural injection, denervation procedure or other procedure for pain management has not been performed at the index level will be summarized at the 3-, 6-, 12-, and 24-month time points. For the 24-month time point, a statistical test will be conducted. The relevant hypothesis is

$$H: p_t - p_c > 0,$$

where p_t and p_c are the proportions of subjects in the treatment and control groups, respectively, who are not taking narcotic medications and have not had pain management procedures at the index level. [REDACTED]

[REDACTED]

Length of Hospital Stay

The length of hospital stay will be calculated for each subject (with the day of surgery = Day 0) and summarized by treatment group. A statistical test of the difference in length of stay between treatment groups will be conducted. The relevant hypothesis is

$$H: \mu_t - \mu_c < 0$$

where μ_t and μ_c are the average stays in the treatment and control groups, respectively. It is anticipated that the distribution of hospital stays will be somewhat skewed, so the data will be ranked and the statistical method will be the Bayesian version of the Wilcoxon Rank-Sum test, described below. If a subject should die in hospital before being discharged, that subject will be assigned a length of stay that is 1 day greater than the maximum observed length of stay for any patient.

Duration of Procedure

The duration of the procedure will be summarized for the treatment and control groups. Statistical summaries will include means, medians, and standards of deviation, as well as 95% credible intervals for μ_t , μ_c , and $(\mu_t - \mu_c)$. A statistical test will be conducted on the hypothesis

$$H: \mu_t - \mu_c < 0$$

where μ_t and μ_c are the average procedure durations in the treatment and control groups, respectively. The statistical method will be the Bayesian version of a t-test, described below.

Instrumentation Time

The portion of the procedure time that is due to Instrumentation Time will be summarized for the treatment and control groups. Statistical summaries will include means, medians, and standards of deviation, as well as 95% credible intervals for μ_t , μ_c , and $(\mu_t - \mu_c)$. A statistical test will be conducted on the hypothesis

$$H: \mu_t - \mu_c < 0,$$

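### A procedure-related, non-device death after completed surgery is not visibly a failure: before 6 months it is predicted like missing data, and later it is ambiguous

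*Combined protocol and SAP*

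**What the plan says.** - **Endpoint (3.5.1 and Protocol Summary).** Success has four visible components: ZCQ, neurological status, no further surgery at the treated level, and "No serious device-related adverse events". In 3.5.1 the last one points to a following paragraph that is redacted. The Protocol Summary words the ZCQ component as "Improvement in the ZCQ by a minimum of 0.5 for both Symptom Severity (SS) and Physical Function (PF) scores at 24 months".
- **Relatedness (6.1.2, 6.1.3).** Procedure and device are graded on separate scales. For the procedure: "The relationship between an adverse event and the surgical procedure (investigational or control treatment) will be assessed on the basis of the following definitions".
- **Discontinuation (5.7).** Death stands beside loss to follow-up and withdrawal of consent under the words "Acceptable reasons for not evaluating a patient through the follow-up period include". No outcome is assigned to it.
- **Prediction (8.4, 8.6).** The primary analysis "will predict 2-year outcomes for any subjects without measured 2-year outcomes, based on transitions from interim states". The cause of the missing value does not matter; loss to follow-up is given as an example. State (c), imputed as failure with certainty, is for patients who can no longer succeed because of an event. Device removal and re-operation are its examples. States (a) to (c) are defined for patients who have 6-month or 1-year data.
- **Where the plan does give a rule.** Section 8.1: "Subjects for whom surgery is attempted but not successfully completed will be considered treatment failures". Section 8.7, on hospital stay, ranks such a death beyond the longest stay observed: "If a subject should die in hospital before being discharged, that subject will be assigned a length of stay that is 1 day greater". The return-to-work analysis in 8.7 censors at death.

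**The concern.** The composite is meant to carry safety and effectiveness together. Section 9.1 lists pulmonary embolism, stroke, myocardial infarction and pneumonia as surgical risks, apart from the implant risks in 9.2. A fatal event of this kind, judged related to the operation and not to the implant, triggers no adverse-event component. If the patient is then handled as an ordinary missing value, the primary analysis credits part of a success to someone the operation killed. A patient whose operation could not be finished is a failure outright.

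A second issue is pre-specification. Where the text allows two codings, the choice could be made after the deaths and their arms are known.

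**Working it through.** The documents show no death rate, success-rate assumption or win threshold, so there is no plan figure to reproduce. The rates and death counts below are assumptions.

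**1. Where a procedure-related, non-device death lands, by timing**

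| Time of death | Text that applies | Value in the primary analysis |
|---|---|---|
| Before surgery is completed | 8.1 | Failure |
| After completed surgery, before the 6-month visit | 8.4: no 6- or 12-month data, so not in (a)–(c); 8.6: predicted | Success probability of the no-interim-data state |
| After a 6- or 12-month visit | 8.4(c) if death is read into its open list; otherwise the last observed state | 0, or that state's success probability |

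The second row separates death from the named examples in (c). Under 5.6 a re-operated patient stays in follow-up and can be coded as a failure at the next visit. A patient who died early never reaches that visit.

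**2. Value given at a win look**

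All win looks use Beta(1,1) for the transitions (8.4). With S successes and F failures observed from a state, the mean is (1 + S)/(2 + S + F). I take every patient with a 2-year outcome as informing the no-interim-data state.

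- 70 successes in 100 patients: 71/102 = 0.696.
- 200 AFRS patients, 4 deaths, about 65% success in the other 196 (127 of 196): 128/198 = 0.646.

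So about 0.65 to 0.70 of a success per death.

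**3. Overstatement of the arm's success rate**

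Formula: deaths × value / arm size. At N = 300 the arms are 200 and 100.

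- Low end, AFRS: 2 × 0.65/200 = 0.0065, or 0.65 points.
- High end, AFRS: 4 × 0.70/200 = 0.014, or 1.4 points.
- One control death: 1 × 0.70/100 = 0.007, or 0.7 points, in the opposite direction.

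**4. Effect on the probability of non-inferiority (margin 0.15)**

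Beta-binomial posteriors with flat priors, 400,000 draws, control success 70%, deaths in the AFRS arm only and predicted from the no-interim-data state:

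| N | Assumed AFRS success | AFRS deaths | Deaths predicted | Deaths as failures |
|---|---|---|---|---|
| 300 | 65% | 1 | 0.965 | 0.960 |
| 300 | 65% | 2 | 0.970 | 0.960 |
| 300 | 65% | 4 | 0.964 | 0.941 |
| 300 | 62% | 4 | 0.908 | 0.866 |
| 300 | 60% | 4 | 0.832 | 0.774 |
| 750 | 65% | 10 | 0.998 | 0.993 |

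Compare across a row, not down a column, because whole-patient rounding shifts the observed rate between rows. The gap widens as the observed difference nears the margin.

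**5. Prior means in Table 8.4.2, a/(a + b)**

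411.97/1056.33 = 0.39; 386.55/415.64 = 0.93; 229.80/383.00 = 0.60; 204.00/255.00 = 0.80; 234.50/335.00 = 0.70. These informative priors enter sample-size looks only, so they do not measure the effect on a success claim.

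**The case against.** - **State (c) already covers death.** Its list is open, a dead patient cannot show 24-month ZCQ improvement, and (c) is failure with certainty. This stands for deaths after a 6- or 12-month visit as a fair reading, though not the only one. It does not reach earlier deaths, because (a)–(c) presuppose interim data. The ZCQ argument does not settle those either: 8.6 predicts an unmeasured 2-year outcome and does not fail it.
- **The deciding text may be redacted.** The paragraph that the device-related component points to, and the end of 8.6, are blacked out. This stands, and the finding and fix are conditional on it.
- **Relatedness is adjudicated.** Sections 9.1 and 9.2 are risk lists, the two scales are not mutually exclusive, and the Clinical Events Committee could grade a fatal postoperative event as device-related too. True; the point concerns only deaths that are not so graded.
- **The sensitivity analysis bounds it.** Setting γ to minus infinity makes such patients failures. But that moves deaths together with every other lost patient, and 3.1 allows for 15% loss, so the effect of deaths cannot be isolated.
- **The hospital-stay rule proves little.** It supplies a rank for a rank test. I agree that it is no contradiction; it shows only that death was considered elsewhere.

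**Conclusion.** The point holds in a limited form, at low severity. For a procedure-related, non-device death after completed surgery and before 6 months, the visible rules read literally give a predicted success probability instead of a failure, at interim and final analyses. After a 6- or 12-month visit, the classification is ambiguous.

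With 65–70% success and 2–4 such deaths among 200 AFRS patients and none in control, AFRS success is overstated by about 0.65–1.4 points against a margin of 15. Whether that could change a decision is unknown, since the win threshold is not visible.

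A reader might infer more than the documents support:

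- That every operative death is credited. Deaths before completion of surgery are already failures, and later deaths may fall in (c).
- That the plan has no death rule. Redacted text may contain one.
- That a death earns 0.39 to 0.93 of a success in the efficacy claim. Those prior means never enter a win analysis.
- That the rule always favours AFRS. It favours whichever arm has more deaths relative to its size: with 2:1 allocation, two AFRS deaths (0.65 points at 65% success) and one control death (0.7 points at 70%) nearly cancel.

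**What to change.** Unless the redacted text already does this:

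1. State in 3.5.1 and 8.4(c) that a death before the 24-month assessment, judged device- or procedure-related by the Clinical Events Committee, is a failure imputed with certainty at every look, whether or not 6- or 12-month data exist.
2. Add to 8.6 one sensitivity analysis with all deaths, whatever the cause, as failures, run separately from the γ analysis. This also shows the effect of unrelated deaths, which the primary analysis would go on predicting.

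The cost is one endpoint sentence, one line in the state definition and one extra run. Cause of death and relatedness are already collected (5.7, 6.1.2, 6.1.3, 6.4). If such deaths occur, the reported success rate becomes slightly less favourable.

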8.7 Secondary Objectives

General Considerations for Secondary Objectives

While there are many pre-specified secondary objectives, only the first five are designated as objectives for which FDA-approved labeling claims may be sought, and only for the results measured at the 24-month time point. The rest of the secondary objectives have been pre-specified but are intended to be explanatory and supportive in nature, and not the basis of specific labeling claims.

As indicated in “Analysis Methods for Secondary Objectives,” below, flat or diffuse prior distributions have been identified for all secondary objective analyses. For any hypothesis test, a posterior probability greater than 95% for any hypothesis will be considered to constitute evidence in favor of the hypothesis, in the same sense that a frequentist analysis would reject a null hypothesis when $p < 0.05$ and call it “statistically significant.” However, for the subset of secondary objectives on which labeling claims may be sought, the posterior probability threshold for making the claim is somewhat more stringent. See the section entitled “Multiplicity Considerations,” below.

Zurich Claudication Questionnaire (ZCQ) – Physical Function Domain (PF)

The ZCQ PF domain scores for subjects in each treatment group will be summarized at the 3-, 6-, 12-, and 24-month time points. For the 24-month time point, a statistical test will be conducted. The relevant hypothesis is

$$H: \mu_t - \mu_c < \delta$$

where μ_t and μ_c are the average PF scores in the treatment and control groups, respectively, and δ is the margin of non-inferiority.

[REDACTED]

[REDACTED]

Zurich Claudication Questionnaire (ZCQ) – Symptom Severity Domain (SS)

The ZCQ SS domain scores for subjects in each treatment group will be summarized at the 3-, 6-, 12-, and 24-month time points. For the 24-month time point, a statistical test will be conducted. The relevant hypothesis is

$$H: \mu_t - \mu_c < \delta,$$

where μ_t and μ_c are the average SS scores in the treatment and control groups, respectively, and δ is the margin of non-inferiority.

[REDACTED]

[REDACTED]

Back Pain on Visual Analog Scale (VAS)

The back pain VAS scores for subjects in each treatment group will be summarized at the 3-, 6-, 12-, and 24-month time points. For inference, the relevant hypothesis is

$$H: \mu_t - \mu_c < 0,$$

where μ_t and μ_c are the average back pain VAS scores for subjects in the treatment and control groups, respectively. [REDACTED]

SF-36 Physical Composite Score (PCS)

The SF-36 PCS scores for subjects in each treatment group will be summarized at the 3-, 6-, 12-, and 24-month time points. For the 24-month time point, a statistical test will be conducted. The relevant hypothesis is

$$H: p_t - p_c > -\delta,$$

where p_t and p_c are the proportions of subjects in the treatment and control groups, respectively, who improve by at least 15% relative to baseline. [REDACTED]

SF-36 Mental Composite Score (MCS)

The SF-36 MCS scores for subjects in each treatment group will be summarized at the 3-, 6-, 12-, and 24-month time points. For the 24-month time point, a statistical test will be conducted. The relevant hypothesis is

$$H: p_t - p_c > -\delta,$$

where p_t and p_c are the proportions of subjects in the treatment and control groups, respectively, who improve by at least 15% relative to baseline.

Radiographic Assessment of Flexion-Extension Range of Motion

Assessment of Flexion-Extension Range of Motion for subjects in each treatment group will be summarized at baseline and at each of the 3-, 6-, 12-, and 24-month time points. At 24 months, a statistical test will be conducted. For inference, the relevant hypothesis is

$$H: \mu_{T(24)} - \mu_{T(B)} > 0,$$

where $\mu_{T(24)}$ and $\mu_{T(B)}$ are the average flexion-extension range of motion scores for subjects in the treatment group at 24 months and baseline, respectively.

Radiographic Success

Radiographic Success rate will be summarized for each treatment group at the 3-, 6-, 12-, and 24-month time points. For the 24-month time point, a statistical test will be conducted. The relevant hypothesis is

$$H: p_t - p_c > -\delta,$$

where p_t and p_c are the proportions of subjects in the treatment and control groups, respectively, who achieve radiographic success.

Neurological Assessment

A neurological assessment will be conducted at 3-, 6-, 12-, and 24-months, and summarized. For the 24-month time point, a statistical test will be conducted. The relevant hypothesis is

$$H: p_t - p_c > -\delta,$$

where p_t and p_c are the proportions of subjects in the treatment and control groups, respectively, whose neurological assessment status relative to baseline is maintained or improved.

Leg Pain on Visual Analog Scale (VAS)

The leg pain VAS scores for subjects in each treatment group will be summarized separately by the more symptomatic and less symptomatic legs of each subject, as measured at baseline. For inference, the relevant hypothesis is

$$H: \mu_t - \mu_c < 0$$

where μ_t and μ_c are the average VAS scores for the more symptomatic legs (or less symptomatic legs, as appropriate) in the treatment and control groups, respectively.

Oswestry Disability Index (ODI)

The ODI scores for subjects in each treatment group will be summarized at the 3-, 6-, 12-, and 24-month time points. For the 24-month time point, a statistical test will be conducted. The relevant hypothesis is

$$H: \mu_t - \mu_c < \delta$$

where μ_t and μ_c are the average ODI scores in the treatment and control groups, respectively.

[REDACTED]

[REDACTED]

Adverse Events

All Adverse Events (AEs) will be tabulated and summarized as counts and percentages by treatment group. AEs will also be cross-tabulated separately according to treatment group and:

- Severity (Mild, Moderate, Severe)
- Seriousness (Serious, Non-serious)
- Device-Relatedness (Related, Not Related)
- Surgery-Relatedness (Related, Not Related)

In addition, the occurrence of any Unanticipated Adverse Device Effects (UADE) will be listed. The classification of severity, relatedness, and anticipated nature of AEs will be made by the Clinical Events Committee (CEC).

Summaries will include counts, percentages, and 95% Bayesian credible intervals for the difference in proportions between treatment groups. An analysis of safety outcomes which combines all AFRS treated patients (randomized and non-randomized) compared to control patients will also be performed. The statistical method for dichotomous outcomes (e.g., device-relatedness, surgery-relatedness) will be the Bayesian version of a comparison of proportions, described below. The statistical method for trichotomous outcomes (e.g., Severity) will be the Bayesian version of a comparison of polytomous outcomes, described below.

Surgical Revisions, Reoperations, Removals, and Supplemental Fixation

The incidence of a composite of surgical revisions, reoperations, removals, and supplemental fixation at the index level for subjects in each treatment group will be summarized at the 3-, 6-, 12-, and 24-month time points. For the 24-month time point, a statistical test will be conducted. The relevant hypothesis is

$$H: p_t - p_c < 0$$

where p_t and p_c are the proportions of subjects in the treatment and control groups, respectively, who experience one or more of the defining surgical events. The statistical method will be the Bayesian version of a comparison of proportions (with predictions), described below.

Radiographic Measurements

[figure not shown]
Radiographic measurements in each treatment group will be summarized at the 3-, 6-, 12-, and 24-month time points. Continuous radiographic endpoints are disc height, vertebral range of motion, and translation. For these, statistical summaries will include means, medians, standards of deviation, and 95% central Bayesian credible intervals for the means and mean differences over time between treatment groups, where appropriate. Dichotomous radiographic endpoints are fusion, device migration, and the presence of radiolucencies around the hardware and screws. For these, statistical summaries will include proportions and 95% Bayesian credible intervals for the proportions and, where appropriate, the difference in proportions between treatment groups.

Return to Normal Activities of Daily Life

The proportion of subjects able to return to “Most” or “All” of the activities of daily life will be summarized at the 3-, 6-, 12-, and 24-month time points. Statistical summaries will include proportions and 95% Bayesian credible intervals for the proportions and the difference in proportions between treatment groups. The statistical method will be the Bayesian version of a comparison of proportions, described below.

Return to Work

For subjects in each treatment group, the time from date of surgery to date of return to work will be computed and summarized with descriptive statistics. It is possible that some subjects will never return to work and be censored in this analysis, either at the end of the study or at the point of death or loss to follow-up, so the statistical technique will be the Bayesian Survival Analysis, described below.

[REDACTED]

[REDACTED]

[REDACTED]

[REDACTED]

ZCQ Patient Satisfaction Domain Score

The ZCQ Patient Satisfaction domain scores will be summarized for subjects in each treatment group at the 3-, 6-, 12-, and 24-month time points. For the 24-month time point, a statistical test will be conducted. The relevant hypothesis is

$$H: \mu_t - \mu_c > 0$$

where μ_t and μ_c are the average satisfaction scores in the treatment and control groups, respectively. [REDACTED]

[REDACTED]

[REDACTED]

Narcotic Medication Usage

The proportions of subjects in each treatment group who are not on narcotic pain relieving medications and in whom an epidural injection, denervation procedure or other procedure for pain management has not been performed at the index level will be summarized at the 3-, 6-, 12-, and 24-month time points. For the 24-month time point, a statistical test will be conducted. The relevant hypothesis is

$$H: p_t - p_c > 0,$$

where p_t and p_c are the proportions of subjects in the treatment and control groups, respectively, who are not taking narcotic medications and have not had pain management procedures at the index level. [REDACTED]

[REDACTED]

Length of Hospital Stay

The length of hospital stay will be calculated for each subject (with the day of surgery = Day 0) and summarized by treatment group. A statistical test of the difference in length of stay between treatment groups will be conducted. The relevant hypothesis is

$$H: \mu_t - \mu_c < 0$$

where μ_t and μ_c are the average stays in the treatment and control groups, respectively. It is anticipated that the distribution of hospital stays will be somewhat skewed, so the data will be ranked and the statistical method will be the Bayesian version of the Wilcoxon Rank-Sum test, described below. If a subject should die in hospital before being discharged, that subject will be assigned a length of stay that is 1 day greater than the maximum observed length of stay for any patient.

Duration of Procedure

The duration of the procedure will be summarized for the treatment and control groups. Statistical summaries will include means, medians, and standards of deviation, as well as 95% credible intervals for μ_t , μ_c , and $(\mu_t - \mu_c)$. A statistical test will be conducted on the hypothesis

$$H: \mu_t - \mu_c < 0$$

where μ_t and μ_c are the average procedure durations in the treatment and control groups, respectively. The statistical method will be the Bayesian version of a t-test, described below.

Instrumentation Time

The portion of the procedure time that is due to Instrumentation Time will be summarized for the treatment and control groups. Statistical summaries will include means, medians, and standards of deviation, as well as 95% credible intervals for μ_t , μ_c , and $(\mu_t - \mu_c)$. A statistical test will be conducted on the hypothesis

$$H: \mu_t - \mu_c < 0,$$

where μ_t and μ_c are the average instrumentation times in the treatment and control groups, respectively. The statistical method will be the Bayesian version of a t-test, described below.

Procedural Blood Loss

The blood lost by subjects during the implant procedure will be summarized for the treatment and control groups. Statistical summaries will include means, medians, and standards of deviation, as well as 95% credible intervals for μ_t , μ_c , and $(\mu_t - \mu_c)$. A statistical test will be conducted on the hypothesis

$$H: \mu_t - \mu_c < 0$$

where μ_t and μ_c are the average blood loss in the treatment and control groups, respectively. The statistical method will be the Bayesian version of a t-test, described below.

Rehabilitation Utilization

The proportions of subjects in each treatment group who utilize rehabilitation therapy will be summarized at the 3-, 6-, 12-, and 24-month time points. A subject will be considered to have used rehabilitation therapy at 6 months if he/she has used rehabilitation therapy at any time between the 3-month and the 6-month visits, and similar for each of the other time points. A statistical test will be conducted for each time point. The relevant hypothesis is

$$H: p_t - p_c < 0,$$

where p_t and p_c are the proportions of subjects in the treatment and control groups, respectively, who have utilized rehabilitation therapy since the last (surgery to 3 months, 3 months to 6 months, 6 months to 12 months, 12 months to 24 months) follow-up visit. The posterior probability of superiority $\Pr(H | \text{data})$ will be reported. The statistical method will be the Bayesian version of a comparison of proportions, described below.

[REDACTED]

